Visit Plan	For patients under treatment and follow-up at this hospital, no in-person visits are required; relevant data can be obtained from the electronic medical record (EMR) system and imaging system of this hospital. For patients not receiving treatment at this hospital, a telephone follow-up protocol is implemented to obtain relevant pathological results.

research report	The study plans to enroll 120 eligible patients within 3 years, followed up their pathological results, and conduct statistical analysis.
statistical analysis	Statistical analysis was performed using SPSS 17.0. The diagnostic sensitivity, specificity, and negative/positive predictive values were calculated using a four-cell table. The area under the ROC curve and the optimal cutoff value (SUV optimal cutoff) were evaluated by ROC curve analysis. The consistency between 18F-FAPI PET diagnosis and pathological diagnosis was assessed using the kappa test. A p-value <0.05 was defined as statistically significant.

English abbreviation reference

PET	Positron emission tomography
CT	Computed tomography
ROC	Receiver operating characteristic curve
FAPI	Fibroblast activation protein inhibitor

1 Research Background

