5.1 Research Methods

This study adopted a prospective, multicenter research design. It aimed to evaluate the diagnostic research and exploration of 18F-FAPI PET/CT in lung cancer patients. A total of 120 subjects were planned to be enrolled from three centers nationwide (The First Affiliated Hospital of Zhejiang University School of Medicine, Zhejiang Provincial People's Hospital, and Shulan Hangzhou Hospital).

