5.4 Study Endpoints

Primary endpoint: Diagnostic efficacy of 18F-FAPI PET/CT in lung cancer patients (sensitivity, specificity, accuracy)

secondary end points:

- ① Compare the diagnostic performance differences of 18F-FAPI PET/CT with CT, MR, and 18F-FDG PET imaging in clinical applications for lung cancer;
- ② Analysis of diagnostic differences in the subgroup of patients (pathological, genetic, etc.) using 18F-FAPI PET/CT;
- ③ Evaluation of 18F-FAPI PET/CT in predicting lung cancer prognosis.

6 Research Procedures and Operational Standards

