6.2 Subject Screening

Participants will sign an informed consent form prior to enrollment in this study. Investigators will explain the nature, purpose, and risks of the study and provide the participants with an informed consent form. Participants will be given sufficient time to consider the significance of the study before deciding whether to participate. Any modifications to the informed consent form must be notified and approved by the ethics committee prior to participant enrollment.

First, participants must undergo an informed consent process and sign an informed consent form. Subsequently, eligible subjects are screened from the target population according to the pre-established inclusion and exclusion criteria of this study, after which they may be considered for inclusion in the research.

Baseline data collection included general examinations, medical history, and laboratory tests conducted at the same hospital or external hospitals within one week prior to the signing of the informed consent form. Adverse events and concomitant medications were collected after the signing of the informed consent form.

history-taking

Conduct a detailed inquiry into the patient's medical history to clarify symptoms, signs, and prior medical history (e.g., tumor history, surgical history, biopsy history, radiotherapy history, chemotherapy history, family history,

allergy history, etc.), relevant laboratory tests, previous imaging findings (including plain radiography, ultrasound, CT, MRI, as well as 18F-FDG PET/CT, PET/MR, etc.), and recent pathological results (including tumor grading and Ki-67 index, etc.), along with the patient's follow-up medical records.

Image judgment criteria

The uptake of imaging agents in tissues or organs that normally do not take up such agents can be considered pathological. Typically, 18F-FAPI is rapidly cleared from the bloodstream. Taking 18F-FAPI as an example, radioactive distribution can be observed in the salivary glands, thyroid, liver, biliary tract, gallbladder, pancreas, adrenal glands, kidneys, intestines, collecting system, and bladder, with almost complete excretion through the biliary tract. There is minimal distribution of the radioactive imaging agent in brain tissue. Compared to the liver, if the uptake is significantly increased in a lesion, it is considered positive, suggesting malignant tumors. Generally, moderate intestinal distribution and non-focal intestinal uptake are considered non-pathological.

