7.1 Total Sample Size

Assuming we obtained the sensitivity (Se) of 0.92, specificity (Se) of 0.96, and disease prevalence (P) of 0.05 from the literature [9-11], we set the allowable error (d) to 0.08, with a confidence level of 95% (Z=1.96). When estimating the sample size using sensitivity, the formula yields

$$N = (1.962 * 0.95 * (1 - 0.95)) / 0.052 = 113$$

The sample size was estimated to be 113 cases according to theoretical calculation.

In addition, based on previous studies, the potential loss-to-follow-up rate for patients is estimated to be 5%-10%. This study anticipates a 10% loss-to-follow-up rate during the clinical trial, with a calculated total sample size of 120 cases. This is a multicenter study, with 80 cases from our center (The First Affiliated Hospital of Zhejiang University School of Medicine), 20 cases from Zhejiang Provincial People's Hospital, and 20 cases from Shulan Hangzhou Hospital.

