7.3 Statistical Methods

Statistical analysis was performed using SPSS 17.0. The diagnostic sensitivity, specificity, and negative/positive predictive values were calculated using a four-cell table. The area under the ROC curve and the optimal cutoff value (SUV optimal cutoff) were evaluated by ROC curve analysis. The consistency between 18F-FAPI PET/CT diagnosis and pathological diagnosis was assessed using the kappa test. A p-value <0.05 was defined as statistically significant.

Statistical analysis was performed using SPSS 17.0.

① Diagnostic performance evaluation, four-grid table index calculation:

Sensitivity = True positives / (True positives + False negatives) × 100%

Specificity = True Negative / (True Negative + False Positive) × 100%

Positive predictive value = true positive / (true positive + false positive)

Negative predictive value = true negative / (true negative + false negative)

② ROC curve analysis:

Calculate the area under the curve (AUC) and evaluate diagnostic performance (AUC>0.9 indicates excellent, 0.8-0.9 indicates good, 0.7-0.8 indicates moderate).

Determine the optimal cutoff for SUV using the maximum Youden index.

③ consistency check

The consistency between 18F-FAPI PET/CT and pathological diagnosis was evaluated using the Kappa coefficient.

Kappa>0.8: Excellent consistency;

0.6-0.8: High consistency;

<0.6: Consistency should be interpreted with caution.

Bilateral test, $p<0.05$ defined as significant difference.

④ survival analysis

Kaplan-Meier method:

Collect baseline PET parameters (lesion SUVmax, lesion SUVmean, MTV, LTV, bone marrow SUVmax, etc.), and plot PFS/OS curves according to treatment response (CR/PR vs. SD/PD), pathological response (e.g., MPR status), or PET parameter grouping (e.g., high/low SUVmax). Compare the significance of survival differences between groups using the Log-rank test ($p<0.05$).

Cox proportional hazards model:

Univariate analysis: Screening of clinical variables associated with PFS/OS (age, stage, SUVmax, MTV, etc.).

Multivariate analysis: Significant univariate variables ($p<0.1$) were included, with quantified hazard ratios (HR) and 95% confidence intervals.

Verify the proportional hazards assumption (Schoenfeld residual test).

8 Data Recording and Management

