8.1 Investigator Data Records

- 1) For all eligible participants who have signed the informed consent form, their relevant data and laboratory test results must be meticulously and thoroughly documented.
- 2) All imaging data were interpreted by two attending physicians with over 5 years of experience in nuclear medicine, and the chief physician provided the final consensus interpretation for any questionable cases.
- 3) Original data records, signed by the investigator and dated.

4) Confirm that all adverse events have been documented, and that serious adverse events have been reported and recorded in accordance with relevant procedures in a timely manner.

9 Expected Research Progress

Study recruitment period: 36 months

Observational study duration: This study was an observational study, with patient mortality serving as the endpoint of follow-up.

10 Adverse Event Assessment and Reporting

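### Section 7.3 picks the SUV cut-off at the Youden maximum in the study's only cohort, so sensitivity and specificity reported at that cut-off will be optimistic

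*Protocol*

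**What the plan says.** Protocol section 7.3 lists its diagnostic analyses as separate items. The opening paragraph says: "The diagnostic sensitivity, specificity, and negative/positive predictive values were calculated using a four-cell table". Item 1 then gives the formulas for sensitivity, specificity and the predictive values. Item 2 covers ROC analysis: the AUC is calculated, and then "Determine the optimal cutoff for SUV using the maximum Youden index". The opening paragraph of 7.3 and the protocol summary both place the threshold in the study's own ROC analysis: "The area under the ROC curve and the optimal cutoff value (SUV optimal cutoff) were evaluated by ROC curve analysis".

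On the data available for this, section 5.1 says: "A total of 120 subjects were planned to be enrolled from three centers nationwide". Section 7.1 adds: "This study anticipates a 10% loss-to-follow-up rate during the clinical trial". The section on loss to follow-up excludes such patients from the diagnostic analysis. No second cohort, split, cross-validation, bootstrap or cut-off taken from outside the study is described.

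A scan is called positive in one place only, under the image judgment criteria in section 6.2: "Compared to the liver, if the uptake is significantly increased in a lesion, it is considered positive, suggesting malignant tumors". Section 8.1 says who reads: "All imaging data were interpreted by two attending physicians with over 5 years of experience in nuclear medicine", with a chief physician settling questionable cases. The primary endpoint in section 5.4 is sensitivity, specificity and accuracy. An SUV threshold is not listed as an endpoint.

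**The concern.** The Youden maximum is the threshold at which the observed sum of sensitivity and specificity is largest. Part of that maximum is real separation between the groups, and part is chance in this particular sample. If performance at the threshold is then read from the same sample, the chance part is counted as performance. The bias runs upward on average and grows as the smaller diagnostic group shrinks. Here that may be the cancer-free group, since patients with already confirmed lung cancer are eligible and no minimum number of cancer-free patients is set.

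At stake is the credibility of a published SUV threshold: its quoted sensitivity and specificity would probably not be matched in new patients. Section 7.3 also does not state in words which call fills the four-cell table, so it is worth asking whether the optimism could reach the primary endpoint.

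**Working it through.** **Plan's own figure.** The protocol gives no performance figure for the SUV cut-off, so there is nothing to reproduce. The size has to be simulated under stated assumptions.

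**Inputs from the protocol.** N = 120 (5.1); about 120 × 0.90 = 108 evaluable after 10% loss (7.1); cut-off at the maximum of sensitivity + specificity − 1 (7.3); planning sensitivity 0.92 and specificity 0.96 (7.1).

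**Assumptions.** SUV is normal with equal variance in both groups, on some scale. The cancer share is 50% to 90%. The AUC runs from 0.75 to 0.987. The upper end is what the plan's own pair implies if both values lie on one such curve: z(0.92) + z(0.96) = 1.405 + 1.751 = 3.156, and Φ(3.156/√2) = Φ(2.23) = 0.987.

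**Method.** In each of 4,000 simulated studies per setting, choose the cut-off c that maximises the observed Youden index (candidates midway between neighbouring values). Record the apparent sensitivity and specificity at c, and the true values at the same c: Se = 1 − Φ(c − μ) and Sp = Φ(c), with μ = √2·Φ⁻¹(AUC). The optimism is the mean of apparent minus true. Optimism in accuracy is the cancer share × sensitivity optimism + (1 − share) × specificity optimism.

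**Results, N = 120.**

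| AUC | Cancer / cancer-free | Youden, apparent v true | Youden optimism | Sensitivity (points) | Specificity (points) | Accuracy (points) |
|---|---|---|---|---|---|---|
| 0.75 | 60/60 | 0.42 v 0.35 | 0.08 | 3.8 | 3.8 | 3.8 |
| 0.75 | 96/24 | 0.45 v 0.34 | 0.10 | 2.0 | 8.3 | 3.3 |
| 0.75 | 108/12 | 0.48 v 0.34 | 0.14 | 1.4 | 13.0 | 2.6 |
| 0.85 | 60/60 | 0.59 v 0.52 | 0.07 | 3.4 | 3.3 | 3.4 |
| 0.85 | 96/24 | 0.60 v 0.51 | 0.09 | 1.8 | 7.2 | 2.8 |
| 0.85 | 108/12 | 0.63 v 0.50 | 0.12 | 1.3 | 11.1 | 2.3 |
| 0.95 | 60/60 | 0.79 v 0.74 | 0.05 | 2.4 | 2.5 | 2.4 |
| 0.95 | 96/24 | 0.81 v 0.74 | 0.07 | 1.2 | 5.7 | 2.1 |
| 0.95 | 108/12 | 0.83 v 0.72 | 0.10 | 1.0 | 9.2 | 1.8 |
| 0.987 | 60/60 | 0.91 v 0.87 | 0.04 | 1.7 | 1.9 | 1.8 |
| 0.987 | 96/24 | 0.92 v 0.87 | 0.05 | 1.0 | 4.2 | 1.6 |
| 0.987 | 108/12 | 0.93 v 0.86 | 0.08 | 0.6 | 7.0 | 1.3 |

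Placing the cut-off on an observed value instead of midway moves the results slightly. The largest difference that matters is specificity at AUC 0.987 with 12 cancer-free patients, which becomes 6.0 points instead of 7.0.

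**Worked example at N = 108.** With 70% cancer, AUC 0.90 and the cut-off on an observed value, apparent v true sensitivity is 0.835 v 0.810 (2.5 points) and specificity 0.853 v 0.808 (4.5 points). Accuracy optimism is 0.7 × 2.5 + 0.3 × 4.5 = 3.1 points. With N of 108 or 120 and AUC 0.80 to 0.95, the apparent Youden index exceeds the true one in about 83% to 90% of simulated studies.

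**Which call fills the primary table.** Setting the sections side by side: 6.2 gives a visual rule and is the only text to call a scan positive; 8.1 assigns the reading to physicians; in 7.3 the four-cell table is item 1 and the SUV threshold comes later, under item 2. Nothing ties the table to the threshold. No sentence ties it expressly to 6.2 either.

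**The case against.** Choosing a threshold by the Youden index is a standard exploratory step, and the protocol never claims that the cut-off is validated. It does not say outright that sensitivity and specificity will be reported at the cut-off. Optimism correction could also stand in a statistical analysis plan that is not shown. These points limit the weight of the finding but do not remove it. The protocol fixes the selection rule, in a single cohort, and a threshold described as optimal is normally reported with its sensitivity and specificity. The objection is to reading those figures uncorrected, not to the Youden index.

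A fair critic would add that the Youden index is not an endpoint, that accuracy moves by only 1 to 4 points, and that at the AUC implied by the plan's own planning values the Youden optimism is only about 0.04 to 0.08. All of this stands. The largest figures need about 12 cancer-free patients, a case mix that the protocol does not state, and specificity from so few patients would be imprecise anyway.

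A reader might go further and infer that the primary sensitivity, specificity and accuracy are themselves overstated, or that two competing positivity rules let the better pair be reported as primary. The protocol does not support that. Section 6.2 supplies the only rule that defines a positive scan, and the SUV threshold is neither an endpoint nor linked to the four-cell table. What remains is a missing cross-reference, which calls for clarification and is not evidence of a biased primary endpoint.

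**Conclusion.** The point holds for the figures reported at the SUV cut-off. Selecting and judging the threshold in the same 108 to 120 patients makes its sensitivity and specificity optimistic on average. Under binormal SUVs, AUC 0.75 to 0.987 and 50% to 90% cancer, the overstatement is about 0.04 to 0.14 on the Youden index and about 1 to 4 points on accuracy. It falls mainly on specificity, at about 7 to 13 points, when only about 12 patients are cancer-free. The direction is a general property of the method. The size depends on an AUC, a distribution and a case mix that the protocol does not give. The AUC estimate carries none of this bias. The primary endpoint would carry it only if the Youden cut-off filled the four-cell table, which is not the natural reading.

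**What to change.** In section 7.3, item 2, label the SUV cut-off exploratory. Report its sensitivity and specificity with bootstrap optimism correction, re-selecting the cut-off within every resample, and give a bootstrap interval for the cut-off itself. In the same edit, add one sentence to item 1 confirming that the primary four-cell table uses the visual liver-referenced call from section 6.2, as read under section 8.1, and not the Youden cut-off.

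The cost is a few lines of text and some extra analysis work, with no additional patients, scans or visits. The corrected figures at the cut-off will usually look slightly less favourable.

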2.1.4 Evaluation of 18F-FAPI PET/CT in Predicting Lung Cancer Prognosis

Based on TNM staging and PERCIST criteria, this study evaluates the post-treatment reassessment, efficacy prediction, and prognostic assessment (AUC comparison of PFS/OS) of 18F-FAPI PET/CT in lung cancer. The research will analyze the monitoring capability of 18F-FAPI PET/CT in assessing tumor response post-treatment

and its value in prognostic evaluation, aiming to provide clinicians with a more precise tool for assessing treatment efficacy. It tracks the time from diagnosis to specific events (e.g., CR, PR, SD, PD, recurrence, death) in lung cancer patients to identify influencing factors. Survival rates over time are plotted using Kaplan-Meier curves to visually compare survival differences across groups. Additionally, Cox proportional hazards model multivariate regression quantifies the contribution of factors such as age and pathological stage to survival risk, aiding clinical decision-making.

3 Mechanism of Action and Research Scope of 18F-FAPI PET/CT

18F (97% β^+ , $T_{1/2}=109.7$ minutes) is currently the most widely used radionuclide in PET/CT due to its chemical, physical, and nuclear properties, making it an ideal choice for peptide-based imaging. 18F-FDG is the most commonly used PET tracer in oncology, serving as the preferred modality for tumor diagnosis and therapeutic efficacy evaluation. However, 18F-FDG PET/CT exhibits relatively low sensitivity and specificity for tumors with low invasiveness, high differentiation, or mucinous tissue, while physiological uptake in organs such as the oropharynx and digestive tract often obscures tumor metabolism and uptake. Additionally, mediastinal and hilar lymph nodes still show a high rate of false positives on 18F-FDG PET, whereas 18F-FAPI PET/CT improves the specificity of lymph node diagnosis. Furthermore, compared to 68Ga-labeled tracers, 18F-labeled FAPI has better resolution potential due to its lower positron energy. Therefore, 18F-labeled FAPI holds significant clinical value and promising prospects.

4 Indications, Contraindications, and Precautions

4.1 Eligibility Criteria: Patients with suspected or confirmed lung cancer who have undergone 18F-FAPI PET/CT

4.2 Exclusion Criteria:

- (1) Concurrent presence of other active malignant tumors or a history of other malignant tumors within the past 5 years;
- (2) Severe uncontrollable diseases or active infections;
- (3) Ineligible participants for informed consent.

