5.3 Subject Selection

5.3.1 Eligibility Criteria for Subjects

- (1) Patients with suspected or confirmed lung cancer
- (2) 18F-FAPI PET/CT has been performed.

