7.2 Significance Level and Power of Clinical Studies

The significance level α was set at 0.05; the confidence level was 0.95.

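### PFS is compared by log-rank between CR/PR and SD/PD although progression is itself the PFS event, so the comparison favours responders by construction

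*Protocol*

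**What the plan says.** Protocol section 7.3, item ④ (survival analysis), instructs the analyst to "plot PFS/OS curves according to treatment response (CR/PR vs. SD/PD", and offers pathological response and PET-parameter level as other groupings. It continues: "Compare the significance of survival differences between groups using the Log-rank test", at p<0.05.

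Section 2.1.4 bases response on PERCIST with reassessment after treatment. It gives the only time origin in the document: "It tracks the time from diagnosis to specific events (e.g., CR, PR, SD, PD, recurrence, death) in lung cancer patients". This is a general statement about tracking, not a definition of PFS.

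No landmark, time-dependent handling of response, or restriction to patients still progression-free at the reading appears anywhere. No time for the response reading is fixed. Prognosis is secondary endpoint ③ (sections 2.1 and 5.4).

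**The concern.** The groups are formed from information that arises after the clock has started, and one of the labels is the outcome itself. A patient classed as PD has already had a progression event. A patient classed as CR/PR cannot have progressed before the reading that gave the label. All progressions up to the reading are thus assigned to SD/PD, and responders are credited with event-free time that they could not have lost.

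A later choice of time origin does not cure this. Any origin before the reading gives the same bias, and an origin at the reading gives PD patients an event at time zero. The fault lies in the grouping.

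At stake is one comparison under secondary endpoint ③. It can show responders with longer PFS when response says nothing about later progression, so a significant result could not be interpreted.

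**Working it through.** The protocol states no event count, hazard ratio or power for the survival analysis, so there is no figure to reproduce. The check asks what the planned test returns when response is unrelated to later PFS.

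**Inputs from the protocol.** Log-rank test with α = 0.05 (sections 7.2 and 7.3), taken as two-sided; 7.3 specifies a two-sided test under its consistency check. Total 120 patients with 10% loss to follow-up (7.1), so 120 × 0.9 = 108. That is an upper bound on the number evaluable for response, because section 5.3.1 admits "Patients with suspected or confirmed lung cancer". Values of 60 and 40 were therefore also used.

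**Assumed inputs, none in the protocol.** Exponential PFS with the same hazard for everyone; median 6, 12, 18 or 24 months; one response reading at 2 or 3 months; 40% CR/PR, allocated at random among patients event-free at the reading; uniform censoring at 6 to 36 months; progression before the reading = PD; deaths before the reading (20% of events) excluded.

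**By hand, per 100 patients** (median 6 months, reading at 3 months, no censoring, all early events counted as PD):
- Hazard λ = ln 2 / 6 = 0.1155 per month for every patient; mean time 1/λ = 8.656 months.
- Event by 3 months: 1 − 2^(−3/6) = 29.3%. The other 70.7 split into 28.3 CR/PR and 42.4 SD.
- Mean time if event-free at 3 months: 3 + 8.656 = 11.656 months. Mean time if PD: 8.656 − 3 × 0.7071/0.2929 = 1.414 months.
- CR/PR event rate: 1/11.656 = 0.0858.
- SD/PD event rate: 71.7 / (42.4 × 11.656 + 29.3 × 1.414) = 71.7/536 = 0.1338.
- Apparent rate ratio: 0.0858/0.1338 = 0.64. The true value is 1.

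**Simulation, 4000 trials per scenario.** Two-sided log-rank rejection rate, with median hazard ratio in brackets, for the comparison as written:

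| Reading | n | Median PFS 6 | 12 | 18 | 24 months |
|---|---|---|---|---|---|
| 3 months | 108 | 0.488 (0.63) | 0.235 (0.71) | 0.156 (0.75) | 0.122 (0.77) |
| 3 months | 60 | 0.306 (0.62) | 0.135 (0.71) | 0.110 (0.74) | 0.079 (0.77) |
| 3 months | 40 | 0.185 (0.62) | 0.100 (0.70) | 0.080 (0.74) | 0.071 (0.76) |
| 2 months | 108 | 0.270 (0.73) | 0.137 (0.80) | 0.101 (0.82) | 0.085 (0.83) |
| 2 months | 60 | 0.151 (0.73) | 0.083 (0.80) | 0.071 (0.82) | 0.068 (0.84) |
| 2 months | 40 | 0.125 (0.72) | 0.082 (0.79) | 0.065 (0.82) | 0.057 (0.83) |

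A landmark at the reading, in the same 24 scenarios, gives rejection of 0.043 to 0.064 and hazard ratios of 0.99 to 1.02. Repeat runs agree with the table to within about three percentage points.

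**Variations.**
- Origin 0 to 2 months earlier (diagnosis before treatment; 3-month reading, n = 108, 2000 runs): rejection 0.492, 0.221, 0.146 and 0.117 for the four medians; hazard ratios 0.63 to 0.77. The earlier origin makes no material difference.
- Reading dates varying over 1.5 to 6 months, n = 40 to 108, 2000 runs: as written, rejection 0.083 to 0.596 and hazard ratio 0.57 to 0.73. With response as a time-dependent covariate, 0.049 to 0.065 and 0.96 to 1.02.
- 40% or 60% responders, medians 6 to 24 months, uniform censoring at 12 to 48 months, no exclusion of early deaths: rejection 0.09 to 0.90 at n = 108 and 0.07 to 0.67 at n = 60; apparent rate ratio 0.53 to 0.84. Landmark: 0.048 to 0.060.

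**The case against.** The protocol never defines PFS, nor does it say that PD by PERCIST is the PFS event. Section 1.3.2 discusses RECIST 1.1 and iRECIST. If progression were judged by another criterion, a PD label need not coincide with an event. This tempers the claim that every PD patient has already had the event. It does not remove the bias, because response is still known only after the origin. An SAP may well define PFS and its origin, but the protocol already fixes this grouping and test, and an SAP that follows it inherits the fault.

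The percentages depend on assumptions. More responders make them worse, as the last variation shows. Longer PFS makes them milder, and early-stage patients are included (section 2.1.3). At a median of 60 months with 40% responders, rejection is 0.047 at n = 40 and 0.059 to 0.066 at n = 108, close to nominal. This stands: the figures are illustrations. Even so, the hazard ratio remains 0.78 to 0.85 where the truth is 1.

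Finally, this is one of three alternative groupings under the third secondary endpoint, and no sample size rests on it. That limits the importance of the point, not its correctness.

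**Conclusion.** The concern holds. As written, the comparison favours CR/PR by construction. The direction is certain; the size is conditional. With 40% responders, a reading at 2 or 3 months and median PFS of 6 to 24 months, the spurious hazard ratio is 0.62 to 0.84. The false-significance rate is 9% to 49% at n = 108, 7% to 31% at n = 60 and 6% to 19% at n = 40. With medians of 12 to 24 months and 40 to 60 evaluable patients, it is 6% to 14%, near nominal at the low end, while the hazard ratio stays at 0.70 to 0.84.

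The point is confined to PFS by treatment response. The baseline PET-parameter curves, the Cox variables named in 7.3 (age, stage, SUVmax, MTV) and the primary endpoint are unaffected. Bias in OS by response has not been shown. The change should be made, but the trial's main result does not depend on it.

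**What to change.** In section 7.3, item ④, replace PFS by CR/PR v SD/PD with one of the following.

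- **(a) Landmark analysis.** Start the clock at a named response-assessment time, among patients alive and progression-free then. State that for PFS this compares CR/PR with SD, because PD patients leave the comparison. This keeps a Kaplan-Meier plot and log-rank test.
- **(b) Time-dependent covariate.** Enter CR/PR in the Cox model, switched on at each patient's own reading date, with PD counted only as an event. This keeps all patients and needs no common reading time, but supplies no replacement curve.

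As a precaution only, OS by response can start at the same time point among patients then alive. PD patients should stay in that OS comparison.

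**Cost.** Option (b) needs revised analysis wording and the date of each response reading. Option (a) also needs a common reading time, which the protocol does not now have, and it loses patients with an event before the landmark. That share is 1 − 2^(−L/median): for medians of 6, 12, 18 and 24 months, about 29%, 16%, 11% and 8% at L = 3 months, or 21%, 11%, 7% and 6% at L = 2 months. Neither option changes enrolment or the sample size.

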1.3.3 The Importance of 18F-FAPI PET/CT in Prognostic Prediction of Lung Cancer

There is a significant correlation between imaging features and tumor mutational burden (TMB), and imaging assessment can serve as an effective tool for predicting immune therapy response [26]. This combination not only improves the accuracy of efficacy prediction but also provides new insights for personalized treatment. However, as an emerging imaging technology, 18F-FAPI PET/CT still requires further research in predicting patient prognosis and treatment response.

Based on this, the present study adopted a prospective, multicenter research design to evaluate the diagnostic efficacy and prognostic value of 18F-FAPI PET/CT in lung cancer.

2 Objectives and Content of Clinical Research

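### Protocol 2.1.4 names efficacy prediction by FAPI PET/CT as an aim, but no analysis in 7.3 has treatment response or MPR as its outcome

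*Protocol*

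**What the plan says.** Section 2.1.4 of the protocol says that "this study evaluates the post-treatment reassessment, efficacy prediction, and prognostic assessment (AUC comparison of PFS/OS) of 18F-FAPI PET/CT in lung cancer". That is three aims, and the PFS/OS comparison is attached to the third. The rationale in 1.3.3 also treats response as a target of prediction in its own right: it says that FAPI PET/CT "still requires further research in predicting patient prognosis and treatment response".

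The formal endpoint lists (2.1 Objectives of Clinical Research, and 5.4) are narrower. The third secondary endpoint reads "Evaluation of 18F-FAPI PET/CT in predicting lung cancer prognosis" and does not mention response.

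In 7.3, under survival analysis, the Kaplan-Meier plan is to collect baseline PET parameters and "plot PFS/OS curves according to treatment response (CR/PR vs. SD/PD), pathological response (e.g., MPR status". The same sentence then offers a third grouping, "or PET parameter grouping (e.g., high/low SUVmax". The Cox step begins with "Screening of clinical variables associated with PFS/OS (age, stage, SUVmax, MTV, etc".

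**The concern.** To show that a scan predicts efficacy, response has to be the outcome and a scan measurement taken before treatment has to be the predictor. Section 7.3 gives response and MPR the opposite role: they explain survival. A log-rank test of OS by MPR status asks whether patients with a pathological response live longer, and the answer is the same whatever the FAPI scan showed.

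Two things are at stake. Followed as written, the study would collect response, MPR and baseline uptake without relating them, and so could not answer one of its own stated questions. And a clear separation between responders and non-responders, in a section meant to serve the FAPI prognosis endpoint, could be misread as support for FAPI.

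**Working it through.** The plan gives no figure on this point to reproduce. The check is to trace outcome and explanatory variable through each block of 7.3.

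| Block in 7.3 | Outcome or reference | Explanatory variable | Response or MPR as outcome? |
|---|---|---|---|
| 1. Four-cell table | Pathological diagnosis | FAPI reading | No |
| 2. ROC curve | Diagnosis ("Calculate the area under the curve (AUC) and evaluate diagnostic performance") | SUV | No |
| 3. Kappa | Pathological diagnosis | FAPI reading | No |
| 4. Kaplan-Meier and Cox | PFS/OS | Response, MPR or PET-parameter group; age, stage, SUVmax, MTV | No |

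**Tally.** Response or MPR is the outcome in 0 of 4 blocks. It is used in 1 of 4, as a grouping factor.

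**Could another passage fill the gap?** Section 2.1.4 lists CR, PR, SD and PD among events timed from diagnosis, which might suggest response as an outcome. The methods named directly after it are Kaplan-Meier survival curves and a Cox model of survival risk, so the outcome is again survival.

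**What each survival grouping can say about FAPI.**

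- *PET-parameter group:* direct information, because the groups are formed from the FAPI scan.
- *MPR:* none. MPR is read from the resected specimen.
- *CR/PR vs SD/PD:* this depends on how response is read. Section 2.1.4 mentions PERCIST and post-treatment reassessment, which allows a FAPI reading. Section 7.3 does not say so, and 5.3.1 asks only that one FAPI PET/CT has been done, so a second scan is not required. Even if response is read on FAPI, the curve addresses reassessment after treatment and not prediction before it.

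**Time origin.** Section 2.1.4 counts time from diagnosis, while response and MPR become known later. A patient must survive to the assessment to be classified, so responders are credited with time in which they could not have died. If progression counts as a PFS event, a PFS comparison of CR/PR with a group that contains PD is also partly circular.

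**Precision an added analysis might have.** The documents do not give the number of treated patients with a pre-therapy scan and a recorded response, so the inputs are assumptions: AUC A = 0.70; 60 patients, or 108 (120 × 0.90, an upper bound at the planned 10% loss, with every remaining patient usable); 30% or 50% responding. The Hanley-McNeil standard error, with n1 responders and n0 non-responders, is

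SE = √{[A(1−A) + (n1−1)(q1−A²) + (n0−1)(q2−A²)] / (n1·n0)}, with q1 = A/(2−A) = 0.538 and q2 = 2A²/(1+A) = 0.576.

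For n1 = n0 = 30: SE = √[(0.21 + 29 × 0.0485 + 29 × 0.0865)/900] = 0.068, and 1.96 × 0.068 = 0.133.

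| Patients | Response rate | 95% CI half-width for AUC 0.70 |
|---|---|---|
| 60 | 30% | 0.153 |
| 60 | 50% | 0.133 |
| 108 | 30% | 0.114 |
| 108 | 50% | 0.098 |

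On these assumptions the estimate is usable as exploratory evidence but not precise. The MPR subset would be smaller and less precise still.

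**The case against.** The strongest case against has four parts.

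1. *Efficacy prediction is not an endpoint.* It appears in the description of content (2.1.4), with treatment response named again in the rationale, and in neither endpoint list. A model for an exploratory aim is often left to the statistical analysis plan, which is not at hand. This stands as a limit: one can say only that no analysis in 7.3 serves the aim. It does not remove the point, because 7.3 does assign response and MPR a role, and that role is not the one the aim needs.

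2. *The prognosis endpoint is analysed.* This is correct. A reader who stops at the response and MPR groupings might infer that the third secondary endpoint goes untested. The rest of the sentence and the Cox step show otherwise.

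3. *The response grouping may come from FAPI.* This also stands. A reader might infer that two of the three survival groupings carry no FAPI information. The PERCIST and reassessment wording in 2.1.4 does not allow that to be asserted for response; only the MPR grouping is clearly free of FAPI content.

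4. *Responder curves are ordinary descriptive displays.* Section 2.1.4 says that factors influencing survival are to be identified, and nothing in 7.3 says that these curves will be reported as evidence for FAPI. That is fair: misreporting is a risk to guard against and not something the protocol plans. It is also a reason to keep the curves, since the response-grouped one may be the only analysis in 7.3 that can serve post-treatment reassessment.

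**Conclusion.** The point holds in a limited form. Efficacy prediction is a stated aim, and 0 of the 4 analysis blocks in 7.3 can address it, because response and MPR enter only as groupings for PFS/OS. This is a mismatch between a stated aim and the methods. It is not a missing endpoint analysis, and the primary diagnostic endpoint is untouched. The documents do not support saying that FAPI prognosis is untested, or that efficacy prediction will never be tested.

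The conclusion rests on reading the three items in 2.1.4 as distinct aims, which the placing of the PFS/OS comparison and the wording of 1.3.3 support. It depends on no numerical assumption; the AUC half-widths above only indicate what an added analysis might deliver. It is worth correcting before analysis, since the variables needed are ones the protocol already names.

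**What to change.** In 7.3, under survival analysis:

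- **Add** an exploratory analysis with objective response (CR/PR vs SD/PD) as outcome and baseline FAPI SUVmax or MTV as predictor: logistic regression with odds ratio, and AUC, each with a 95% CI. Do the same for MPR among patients resected after neoadjuvant therapy.
- **Restrict** it to patients whose FAPI scan precedes the therapy concerned, and take response from an assessment that does not use the baseline FAPI scan. A response defined as change from baseline FAPI uptake would share its measurement with the predictor.
- **Keep** the response- and MPR-grouped curves as descriptive. State that they are not evidence of FAPI prognostic value unless response was read on FAPI, and start follow-up at the response assessment or at surgery instead of at diagnosis.

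If the sponsor does not intend to study efficacy prediction, the alternative is to delete the phrase from 2.1.4.

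*Cost.* No new scan or visit is needed, but this is more than a change of wording. Eligibility (5.3.1) does not fix when the scan falls relative to therapy, and the Visit Plan in the protocol summary has telephone follow-up of patients treated elsewhere obtain pathological results only. Scan timing and response source therefore have to be recorded, and response may be missing for some patients. The subset is smaller than 120 and of unknown size, and the report should give its number and show the intervals.
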